8.5 Description of Statistical Analyses

8.5.1 General Considerations

The following summary statistics will be used to summarize the trial data per Part and dose level unless otherwise specified:

- Continuous variables: number of not missing observations, mean, standard deviation, median, minimum, and maximum
- Categorical variables: frequencies and percentages.

All summary statistics will be described in detail in the respective Integrated Analysis Plan. There is no formal significance level for this trial and all analyses are considered descriptive.

The cutoff for the analysis will be as follows:

For the analysis after the end of Part 1, the cutoff will be Last Subject Last Visit (LSLV), or 4 months after the last subject enrolled into the monotherapy dose escalation cohort has finished their DLT period, whichever comes first.

For both dose escalation parts, the analysis will focus on the number of subjects experiencing a DLT. The SMC will receive results of a Bayesian two-parameter logistic model with overdose control updated with the observed DLT data for SMCs dedicated to dose escalation decisions ([Babb 1998; Neuenschwander 2008](#)). Recommendation is based on a loss function (probabilities of being in one of the four toxicity probability intervals will be multiplied with a loss term as follows:

$$0 * P(\text{target dosing (0.17-0.33)}) + 1 * P(\text{for over (0.33-0.67] or under dosing [0-0.17]}) + 2 * P(\text{excessive dosing (0.67-1]}).$$

Glossary:

(x.xx-y.yy] = lower limit excluded, upper limit included in the penalties
[x.xx-y.yy] = lower limit included, upper limit included in the penalties

In addition, only doses that have a corresponding probability of less than 25% that the true DLT rate is more than 33% (overdose control) are recommended by the model. The recommended dose level from the Bayesian model for the next cohort is the dose with the lowest loss function from all doses fulfilling the overdose control rule.

- MTD definition

The target DLT rate for the MTD definition is 30%. The MTD suggested by the model (if reached) will be defined as follows:

Highest tested dose with estimated DLT rate $\leq 30\%$. Additionally, the following needs to be fulfilled:

- The upper bound of the 95% credible interval of a potential MTD is not more than 40% and
- The estimated DLT probability for the suggested MTD is above or equal to 17%.

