The SMC will be notified of a potential MTD if a tested dose fulfills the above last 2 criteria. The SMC defines the MTD and can deviate from the suggestion of the model.

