Section 6.5.5 (Management of specific adverse events...)	List anticipated M8891 toxicities based on nonclinical data.	Clarification
Section 6.8 (IMP Accountability)	Clarification to collection of accountability forms	Clarification
Section 7.3 (Efficacy assessments)	Time points for efficacy assessments have been accurately defined	Clarification
Section 7.4.1.3 (Definition of the Adverse Event Reporting Period)	The window period of the EOT visit and the safety follow-up period has been updated	Clarification
Section 7.4.3 (Clinical laboratory assessments) Section 7.5. (Pharmacokinetics)	Reference to blood volumes in Laboratory Manual	Clarification
Section 7.4.4 (Vital signs, physical examinations, and other assessments); Section 8.5.5 (Analysis of other endpoints)	Physical exam no longer includes a complete neurological exam	Medical evaluation that this is no longer warranted.
Section 7.4.5 (Electrocardiograms)	New Section 7.4.5 that includes an updated explanation of ECG evaluations.	Clarity: Part 1 ECGs for QTcF interval evaluation; Part 2 Safety ECGs
Section 8.4	Revised dose limiting toxicity as included in Dose Escalation analysis set.	Clarification and consistency with the ongoing data analysis
Section 8.5 (Statistics)	Subsections reordered	Improve flow of text.
Section 8.5.1 (General considerations)	Updated to include the new timing for the Part 1 analysis and the definition of MTD	Clarification
Section 8.5.2 (Efficacy analysis)	Added information on confidence intervals for all the study and posterior probabilities for Part 2	Clarification on the statistical analysis plan for efficacy
Section 8.5.3 (Safety analysis)	Safety analysis for Part 1 has been updated to include when subject replacement will be considered	Clarification
Section 8.5.3. (Safety analysis)	Addition of posterior probabilities for DLT analysis in Part 1	Clarification on the statistical analysis plan for safety
Section 8.6 (Interim and additional planned analyses)	Updated to include the new timing for the Part 1 analysis	Clarification

Section # and Name	Description of Change	Brief Rationale
Section 11 (References cited)	References added	To support new text, primarily related to Part 2
Appendix II	Updated to include more details on pan-inhibitors that simultaneously inhibit CYP2C9, 2C19 and 3A4	Clarity and relevant to therapy with cabozantinib

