The purpose of this Integrated Analysis Plan (IAP, referred to as Statistical Analysis Plan in protocol version 2.0 of this study) is to document technical and detailed specifications for the final analysis of data collected for protocol MS1000015-0019. Results of the analyses described in this IAP will partly be included in a Clinical Study Report (CSR) or a separate report (e.g. PopPK analysis). Additionally, the planned analyses identified in this IAP may be included in regulatory submissions or future manuscripts. Any post-hoc, or unplanned analyses performed to provide results for inclusion in a CSR but not identified in this prospective IAP will be clearly identified as such in the CSR.

This IAP does not describe the analyses done for the Safety Monitoring Committee (SMC) meetings. Instead, details can be found in SMC IAP, version 1.0 dated Oct 2017.

The IAP is based upon Section 8 (Statistics) of the trial protocol and is prepared in compliance with ICH E9.

5 Objectives and Endpoints

	Objective	Endpoint	IAP Section
Primary Objective	To determine the maximum tolerated dose (MTD) of M8891 as a single agent in subjects with solid tumors.	Dose limiting toxicities (DLTs) during the first 21-day treatment cycle, based on a predefined set of adverse events (AEs), to determine the MTD.	• 15.1
	To evaluate the safety profile and tolerability of M8891 as a single agent	Incidence and severity of treatment- emergent adverse events (TEAEs), and deaths, including cause of death, from screening up to the End of Treatment visit (EOT).	141516.1
Secondary Objectives		Changes in clinical laboratory measures, electrocardiogram (ECG) measures, vital signs, Eastern Cooperative Oncology Group Performance status (ECOG PS).	
	 To investigate the pharmacokinetic (PK) profile of M8891 as single agent 	 PK parameters of M8891 after QD and BID dosing, as applicable: Cmax, tmax, AUC0-t, AUC0-∞, AUC0-т, t1/2, λz, CL/F, CLss/F, Vz/F, Racc(AUC₁) and Racc(Cma_x) 	

	Objective	Endpoint	IAP Section
	To assess the antitumor activity of M8891 as single agent according to RECIST v1.1	Best overall response (BOR: complete response [CR], partial response [PR], stable disease [SD] or progressive disease [PD]) according to RECIST v 1.1. criteria as assessed by investigators	
		 Clinical benefit defined as CR, PR, and SD for ≥ 12 weeks 	

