15.1 Analyses of Dose Limiting Toxicities (Primary Endpoint)

The dose escalation set will be used for all analyses related to the primary endpoint. The frequency and percentage of subjects experiencing a dose limiting toxicity (DLT) will be summarized by dose group and overall. A listing will be provided as well (details on presented information, see Section 15.2).

In addition, the following will be presented:

• Quantiles (2.5%, 25%, 50%, 75% and 97.5%) for the posterior probability of a subject experiencing a DLT at each of the dose levels used in the study according to the same Bayesian Logistic Model (BLM) as descripted in the SMC IAP, Section 14:

Bayesian two-parameter logistic model:

Prior distribution and likelihood are used to calculate the posterior probabilities based on Bayes theorem.

The likelihood is defined based on a binomial distribution, modelling the rate of subjects with at least 1 DLT.

The prior distribution is set-up as follows:

The relationship between dose and toxicity rate is defined by

$$P(DLT|d_j, \alpha, \beta) = \frac{\exp\left(\alpha + \exp(\beta) * \log\left(\frac{d_j}{d_{ref}}\right)\right)}{1 + \exp\left(\alpha + \exp(\beta) * \log\left(\frac{d_j}{d_{ref}}\right)\right)}$$

Where suggested $d_j \in \{7 \text{ mg}, 12 \text{ mg}, 20 \text{ mg}, 35 \text{ mg}, 60 \text{ mg}, 100 \text{ mg}, 150 \text{ mg}, 210 \text{ mg}\}$ for QD (and (α, β))aere bivariate normally distributed.

the following is be derived:

$$E(\alpha) = \log(0.8/0.2) = 1.386$$

$$E(\beta) = \log((\log(0.33/0.67) - \log(0.8/0.2)) / \log(210/340)) = 1.469$$

Variances are chosen as follows: $Var(\alpha)=2^2$, $Var(\beta)=2^2$, $Cov(\alpha, \beta)=0.2$.

MTD suggestion from the BL model

The MTD as suggested from the modeling will be derived as follows:

- 1) The BLM will be updated with all DLT data from the dose escalation.
- 2) Estimated $E(\alpha)$, $E(\beta)$, $Var(\alpha)$, $Var(\beta)$ and $Cov(\alpha, \beta)$ as well as the estimated curve will be provided.
- 3) The dose with targeted toxicity probability of 30% will be identified using the curve.
- 4) The next lower tested dose will be selected.
- 5) It will be checked whether this dose fulfills the overdose control.

The credibility interval will be provided.

This information will be forwarded to the SMC that will decide on the determination of the MTD. Additionally, the SMC will receive the estimated DLT probability and associated probability quantiles for all other doses tested.

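### The SAP and the protocol give different rules for the Part 1 model-suggested MTD, the DLT population and the data cutoff

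*SAP*

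**What the plan says.** **Model-suggested MTD.** SAP 15.1 updates the Bayesian logistic model with all escalation DLT data, finds the dose with a 30% DLT probability, and selects the tested dose below it. As the last step, "It will be checked whether this dose fulfills the overdose control". It does not say what happens if the dose fails. Protocol 8.5.1 starts from "Highest tested dose with estimated DLT rate" of at most 30% and adds two conditions. One concerns precision: "The upper bound of the 95% credible interval of a potential MTD is not more than 40" (in percent). The other sets a floor for the estimate itself: "The estimated DLT probability for the suggested MTD is above or equal to 17" (in percent). In the protocol, overdose control (less than 25% probability that the true DLT rate exceeds 33%) belongs to the next-cohort recommendation, which is "the dose with the lowest loss function from all doses fulfilling the overdose control rule". On the MTD itself, "The SMC defines the MTD and can deviate from the suggestion of the model".

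**DLT population.** SAP Table 1 drops a subject with more than 4 missed days in Cycle 1 only if the reason was not safety. It has no separate clause for subjects with a DLT. Protocol Table 13 and 8.5.3.1 drop any such subject unless there was a DLT. The SAP's own deviation 604 also uses the DLT exception.

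**Cutoff.** SAP Section 9 cuts 22 days after the last subject's first dose. Protocol 8.5.1 and 8.6.1 cut at last subject last visit or 4 months after the last subject's DLT period, whichever is earlier.

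**Versions.** The SAP is v1.0 of 20 April 2018, and describes itself as "referred to as Statistical Analysis Plan in protocol version 2.0 of this study". The log for Amendment 2 (27 August 2019) records for protocol 8.5.1: "Updated to include the new timing for the Part 1 analysis and the definition of MTD". It also records a revision of the Dose Escalation set in 8.4.

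**The concern.** Finding the MTD is the primary objective of Part 1. A programmer following the SAP and a reader holding the protocol could reach different statements of whether the model suggests an MTD, from models fitted to different subjects. SAP 8.1 leaves final exclusions to the data review meeting, which would have two definitions in front of it. The cutoff decides whether the last-enrolled subjects contribute any post-baseline scan to the main analysis of best response, clinical benefit and PFS. SAP Section 7, where departures from the protocol belong, mentions none of the three.

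**Working it through.** **Inputs.** The model and prior agree in both documents (SAP 15.1, protocol 8.5.3.1): logit P(DLT) = α + exp(β)·log(dose/340), bivariate normal, variances 4 and 4, covariance 0.2. The stated prior means reproduce:

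- E(α) = log(0.8/0.2) = 1.386
- E(β) = log[(log(0.33/0.67) − log(0.8/0.2)) / log(210/340)] = 1.469

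Posteriors were computed by integration on a grid. The 25%/33% threshold comes from protocol 8.5.1, because SAP 15.1 does not restate it. Estimates are posterior means; the protocol does not say mean or median. **All DLT data below are assumed**, except where tied to what the protocol reports.

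**(a) MTD rule.** In each row the dose shown is the candidate under both rules.

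| Assumed data | Dose | Mean | Upper bound | P(>33%) | SAP check | Protocol rule |
|---|---|---|---|---|---|---|
| 36 subjects, 3/3/3/3/3/6/9/6 over 7–210 mg; DLTs 0/0/0/0/0/1/2/3 | 150 mg | 25.8% | 46% | 21.7% | met | fails 40% |
| 0/12 at 7–35 mg, 1/3 at 60, 2/12 at 100, 3/6 at 150 | 100 mg | 23.9% | 42.8% | 15.0% | met | fails 40% |
| As above with 1/6 at 60 | 100 mg | 22.4% | 40.5% | 10.9% | met | fails 40%, narrowly |
| 17 subjects, 3/3/3/3/5 at 7–60 mg, 1 DLT at 60 | 60 mg | 13.0% | 39.2% | 5.4% | met | fails 17% |
| 17 subjects, 5/3/3/3/3 at 7–60 mg, 1 DLT at 60 | 60 mg | 16.3% | 47.8% | 11.1% | met | fails both |
| 0/12 at 7–35 mg, 2/12 at 60, 4/6 at 100 | 60 mg | 20.7% | 39.8% | 9.0% | met | met |

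The 17-subject rows are tied to the protocol's reports of 17 subjects at 7–60 mg with at least 3 per level (Section 3.3.1) and one DLT at 60 mg (Section 5.1.3.2.1). They assume levels 7, 12, 20, 35 and 60 mg and no DLT below 60 mg. Seventeen subjects less 5 × 3 leaves 2 to place, giving 15 allocations. All 15 meet the SAP check (P(>33%) 5.4–11.1%) and fall below the 17% floor (mean 13.0–16.3%).

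**(b) Population.** Five or six of 21 daily doses missed is 5/21 = 23.8% or 6/21 = 28.6%, below the interruption criterion for a DLT in protocol 5.1.3.3 (over 7 days or over 30% of the Cycle 1 dose). That criterion also leaves out AEs due to the disease or concomitant medication, however long the absence. A subject absent for such a reason, with no other DLT, is in the SAP set and outside the protocol set.

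Assume 0/12 at 7–35 mg, 1 DLT at 60 mg, 2/3 at 150 mg, and 12 treated at 100 mg with 1 DLT, one of the others being such a subject. The upper bound at 100 mg is:

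| DLTs at 60 mg | SAP set (1/12) | Protocol set (1/11) |
|---|---|---|
| 1/3 | 39.6% | 41.5% |
| 1/4 | 38.8% | 40.6% |
| 1/5 | 38.1% | 39.9% |
| 1/6 | 37.5% | 39.0% |

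In the first two rows the protocol's own MTD rule changes its answer. In the last two it does not.

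**(c) Cutoff.** Part 1 scans fall on Day 1 of Cycles 3, 5 and 7 (protocol 7.3): days 2×21+1 = 43, 4×21+1 = 85 and 6×21+1 = 127. The SAP cutoff, 22 days after first dose, precedes all three, even with the one-week scan window. With the SAP's 30.4375-day month, the protocol cutoff is at latest 21 + 4×30.4375 = 142.75 days, which covers up to three scans if last subject last visit is not earlier and the subject stays on treatment.

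**The case against.** The mismatch is version lag: an April 2018 SAP could not contain definitions introduced in August 2019, and a later SAP may exist. That explains the conflict but does not resolve it in the documents supplied. SAP Section 6 promises an amendment if combination or expansion parts are added after dose escalation is complete, whereas the protocol lets Part 2A enroll while Part 1 is ongoing.

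The SMC decides the MTD and receives DLT probabilities and quantiles, so it can read off the 40% and 17% checks. This stands, and it limits the effect to what is reported as the model's suggestion.

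On the population, days missed because of a DLT count as safety reasons, so most DLT subjects stay in the SAP set; only one whose absence was for other reasons would be lost. Deviation 604 already states the protocol's rule. Both points stand, but the second also means the SAP contradicts itself.

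The examples are sensitive. The 17-subject case is mid-escalation, where no MTD is expected unless escalation stopped there. The 100 mg cases miss the 40% bound by only 0.5 to 2.8 points, and the population effect vanishes with 1/5 or 1/6 at 60 mg. These limits are accepted. The 36-subject case does not depend on them: its upper bound is 6 points above the limit.

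For the cutoff, DLT counts are essentially unchanged, efficacy is descriptive, and SAP Section 6 plans an update after study completion. The gap therefore concerns the main analysis only.

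**Conclusion.** The concern holds. As supplied, the SAP and the protocol conflict on all three points, and the SAP conflicts with itself on the population. The two MTD rules normally pick the same candidate dose but can disagree on whether the model suggests it. This happens in plausible datasets, including one at the planned 36 subjects; no frequency is claimed, because the DLT data are assumed. The population difference moves the upper bound by about 2 points per subject in the example, so it matters only near 40%. The cutoffs differ by up to about 121 days (142.75 − 22), and the SAP's leaves the last subject with no scheduled post-baseline scan in the main analysis. The MTD itself remains the SMC's decision. This should be corrected before database lock, unless a later SAP has already done so.

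**What to change.** Before database lock, amend SAP 15.1, the Dose Escalation row of SAP Table 1 and the Section 9 cutoff so that they are reconciled with protocol 8.5.1, Table 13 with 8.5.3.1, and 8.6.1. Specifically:

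- one MTD-suggestion rule, stating the consequence of failing each check and whether the estimate is the posterior mean or median;
- one DLT population, with an explicit clause for subjects who had a DLT, consistent with deviation 604;
- one data cutoff.

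Record and justify any intended departure from the protocol in SAP Section 7. If a later SAP already does this, cite it as the governing version.

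The cost is SAP wording only. If the protocol's cutoff is kept, the main data cut comes later, which the protocol already commits to.

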Since the start of Part 1, until the 16 Mar 2019 data cut, a total of 17 subjects with various solid tumors have received M8891 in doses ranging from 7 mg to 60 mg with a minimum of 3 subjects per dose level. Preliminary data from this ongoing Part 1 of the study have shown that the oral exposure of M8891 increased reasonably in direct proportion to the dose up to 35 mg QD, whereas at dose of 60 mg QD exposure seems to increase less than in direct proportion to the dose. No safety concerns have been raised (refer to M8891 IB). QT corrected for heart rate according to Fridericia (QTcF) interval prolongation is currently investigated in the ongoing Part 1 of the study using 12-lead triplicate digital ECGs. There is no preclinical or preliminary clinical evidence that M8891 is leading to QTcF interval prolongation.

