5.1.3.2 Part 2, M8891 combined with Cabozantinib, mRCC

5.1.3.2.1 Part 2A, Dose Escalation

In Part 2A, before Cycle 1 Day 1 of all dose levels, subjects will receive a single dose of M8891 in the morning in fed conditions (Day -1, Cycle 1) and the PK profile of M8891 will be evaluated. Subsequently on Day 1 Cycle 1, subjects will initiate treatment with M8891 combined with cabozantinib QD orally every morning under fasted conditions. Following Cycle 1, all other cycles will start with Day 1 and will include only the 21 days of M8891 combined with cabozantinib.

Subjects will accrue in cohorts of 3 subjects for evaluation of M8891 combined with cabozantinib 60 mg QD (with dosage adjustments to 40 or 20 mg FBE permitted to manage AEs as described in Section 6.5.5). Both drugs will be taken in the morning in fasted conditions. A Bayesian 2-parameter logistic regression model with overdose control will be used to assist the SMC with dose selection for the next cohort and to determine the MTD/RDE of M8891 combined with cabozantinib 60 mg QD for Part 2B.

Three pre-specified dose levels of M8891 are planned (20 mg, 35 mg and 60 mg) combined with 60 mg of cabozantinib. Dose levels may be added or skipped for others that are not part of the pre-specified set but they will never exceed the dose level of M8891 that has already been declared to be safe in Part 1. The dose levels have been chosen based on preliminary data from the ongoing Part 1 of the study. At the time of Amendment 2, M8891 single agent was being investigated at 60 mg QD in subjects with solid tumors. PK^{CC} studies have shown that the 20, 35 and 60 mg QD regimens reached pre-selected exposure (≥ 1500 ng/mL) at steady state while CCI

. Three and 5 Grade ≥ 3 TEAEs have been seen at 20 and 35 mg QD regimen, respectively. One DLT (Grade 4 thrombocytopenia) has been observed in the ongoing 60 mg QD cohort (Refer to the M8891 IB).

Dose escalation of the combination will proceed until the RDE of M8891 is reached in combination with a fixed dose of cabozantinib or dose escalation ends due to occurrence of an MTD, or the SMC decides ending dose escalation following review of safety, tolerability, and PK results, whatever occurs first. The maximum dose of M8891 combined with cabozantinib will not exceed the MTD of M8891 in monotherapy determined in Part 1 of the study.

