As second approach, the MTD as suggested by the frequentist estimation will also be derived:

 All DLT data from the dose escalation will be included in a two-parameter logistic regression model (intercept and slop over log of the scaled dose, no prior; if the model does not converge, it will be reported as not calculable; the program code for this analysis can be found in the TLF shells).

- 2) Steps 3) and 4) of the first approach will be followed.
- 3) The confidence interval for the DLT probability will be provided.

There will also be a plot showing both the observed percentage of DLTs and the 75% quantile for the predicted probability according to the BLM over dose. If the SMC decides to switch from QD to BID dosing, there will be a figure for QD and a figure for BID dosing.

Additionally, the posterior probability of toxicity will be plotted versus the dose, using East.

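### The SAP's frequentist MTD rule checks only convergence, so it can name the top tested dose as MTD by extrapolation, and some software will pass fits that have no finite estimate

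*SAP*

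**What the plan says.** SAP 15.1 gives two routes to a model-suggested MTD. The first updates the Bayesian logistic model. Its step 3 reads "The dose with targeted toxicity probability of 30% will be identified using the curve", step 4 reads "The next lower tested dose will be selected", and step 5 adds "It will be checked whether this dose fulfills the overdose control".

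The second route is introduced with "As second approach, the MTD as suggested by the frequentist estimation will also be derived". Its model is a two-parameter logistic regression: "intercept and slop over log of the scaled dose, no prior; if the model does not converge, it will be reported as not calculable". Then "Steps 3) and 4) of the first approach will be followed". Step 5 is not carried over. A confidence interval for the DLT probability is to be reported but is not part of any rule. The program code is said to be in the TLF shells, which are not among the documents.

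Protocol 8.5.1 sets two further conditions on the Bayesian model's MTD: an estimated DLT probability of at least 17%, and an upper 95% credible bound of at most 40%. Protocol 5.1.3.4 allows for the case where no MTD can be determined. The frequentist route has neither the two conditions nor that outcome.

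**The concern.** Step 4 always looks downward from the 30% dose to a tested dose. If the fitted curve is still below 30% at the highest tested dose, the 30% point is an extrapolation and step 4 returns the highest tested dose. The data then say that the MTD was not reached, while the output names one.

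The convergence check has a separate gap. If every DLT is at the top dose, or there are none, the likelihood has no finite maximum. A fitting routine may nevertheless stop and report convergence because the deviance has stopped changing. The not-calculable rule is then not triggered.

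At stake is a table for the primary endpoint in which a second method seems to support an MTD at the top dose when the data cannot.

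**Working it through.** **The plan's own figures.** The documents give no operating characteristics for the frequentist estimate. The nearest stated figures are the prior means, and both reproduce: log(0.8/0.2) = 1.386, and log((log(0.33/0.67) − log(0.8/0.2))/log(210/340)) = 1.469.

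**Rule as written.** Fit logit P(DLT) = a + b·log(dose/340). The scaling by the 340 mg reference dose (Protocol 8.5.3.1) does not affect the result. The 30% dose is D30 = 340·exp((log(0.3/0.7) − a)/b). Select the largest tested dose below D30.

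**Extrapolation.** Assumed data: 0/3, 0/3, 0/3, 1/6, 0/6 at 7, 12, 20, 35, 60 mg. The fit gives a = −1.388 and b = 0.663 (SE 1.6).
- D30 = 340·exp((−0.847 + 1.388)/0.663) = 340·exp(0.815) = 768 mg.
- The next lower tested dose is 60 mg.
- Fitted logit at 60 mg: −1.388 + 0.663·log(60/340) = −1.388 − 1.150 = −2.537, a rate of 7.3%.

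This fit is ordinary and does not depend on the software. The rate of 7.3% is below the 17% that the protocol requires of the Bayesian MTD.

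**No finite estimate.** Results from R's glm at default settings, one row per dose. Lower doses have 0/3 unless stated.

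| Data | Reported converged | Slope (SE) | D30 (mg) | Dose named |
|---|---|---|---|---|
| 1/5 at 60 mg | yes | 40.6 (73,290) | 60.8 | 60 mg |
| 1/4 at 60 mg | yes | 41.1 (72,377) | 60.4 | 60 mg |
| 1/3 at 60 mg | yes | 41.8 (70,901) | 59.8 | 35 mg |
| No DLTs, 0/6 at 60 mg | yes, no warning | −0.21 (54,836) | 3×10⁻⁵⁰ | none |
| 1/6 at 210 mg, eight doses | no | 62.1 (80,023) | 212.6 | not calculable |

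In the first three rows the fitted top-dose rate equals the raw rate and the lower doses go to zero. The selection therefore depends only on whether the raw top-dose rate is below 30%. In the last row, refitting the same data with one record per subject reports convergence (slope 54.4, SE 21,984, D30 213 mg) and names 210 mg. Whether the safeguard works thus depends even on the data layout.

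**Non-positive slope.** With one DLT at 12 mg only (1/3) and 0/6 at 60 mg, the slope is −1.29 and the fit converges. The rule does not cover this case.

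**How often, under assumptions.** Escalation was simulated with the protocol's prior, loss function, overdose control, cohorts of 3, cap of 42 subjects, at most 12 subjects per dose, and a stop when the 17% and 40% conditions are met. Assumed beyond the documents: no skipping of untested doses, escalation allowed to 210 mg, and seven true curves (the prior mean; 30% at 35, 60, 100 or 150 mg with slope 1.5; 30% at 100 mg with slope 3; flat 5%). Each share is summed over trials with 1–2 DLTs and with 3 or more.
- Top dose named by extrapolation, lowest (prior-mean curve): 0.392×5.6% + 0.600×3.4% = 4.2% of trials.
- Top dose named by extrapolation, highest (flat 5%): 0.632×17.1% + 0.194×61.0% = 22.6%.
- Top dose named from separated data if every such fit is accepted, lowest (30% at 35 mg): 0.133×1.5% + 0.867×10.7% = 9.5%.
- The same, highest (prior-mean curve): 0.392×72.5% + 0.600×20.5% = 40.7%.

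**The case against.** **The code may already deal with separation.** The TLF shells are not available and could check for it. This stands. If separated fits are treated as non-converged, only extrapolation and the non-positive slope remain. A reader might infer that the method will often name the top dose from a slope that does not exist; the documents do not support a frequency, because it turns on unseen code.

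**The trial's own data do not show the failure.** One could combine "a total of 17 subjects with various solid tumors have received M8891 in doses ranging from 7 mg to 60 mg" (Protocol 3.3.1) with "One DLT (Grade 4 thrombocytopenia) has been observed in the ongoing 60 mg QD cohort" (Protocol 5.1.3.2.1) and conclude that Part 1 is already separated. The first is a 16 March 2019 data cut and the second describes the position at Amendment 2, dated 27 August 2019. The split by dose is not given beyond a minimum of 3 per level, and the SAP analysis runs only after escalation is complete, with about 36 evaluable subjects anticipated (Protocol 8.1.1). The 1/5 row is therefore an illustration.

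**Selecting on a raw top-dose rate below 30% resembles the protocol's leading criterion**, the highest tested dose with an estimated rate of at most 30%. That is fair. However, the protocol adds the 17% and 40% conditions, and this route does not.

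**The consequence is limited.** All analyses are descriptive, DLT counts and posterior quantiles are shown alongside, and the SMC defines the MTD and may depart from the model (Protocol 8.5.1). The SAP's sentence on forwarding results to the SMC comes before the frequentist route is introduced. A reader might infer that a wrong dose could be chosen on this estimate; nothing in the documents makes it decisive.

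**Penalised regression is a tempting cure, but it is not required.** Firth's penalty is equivalent to a Jeffreys prior and would weaken the contrast that the SAP sets up by using no prior. It also does not solve the problem: in simulation on the full dose grid (six curves) it still named the top dose in 27–60% of trials, against 27–50% unpenalised. For 1/3 at 60 mg it puts the 30% dose at 61.9 mg.

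**Conclusion.** The gap is real and follows from the text: convergence is the only failure rule, and no condition ties the 30% dose to the tested range. Extrapolation to the top tested dose needs no assumption about software, and the 768 mg example shows it. The failure under separation or with no DLTs is possible but conditional, since the same data can pass or fail the convergence check.

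Under the assumed curves, extrapolation alone names the top dose in about 4–23% of trials. That range depends on those curves and on the no-skipping assumption; the worked fits depend only on the data assumed for each. The effect is a misleading supporting output for the primary endpoint. It is worth correcting because the correction is small.

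**What to change.** Add to step 2 of the second approach in SAP 15.1:

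> If there are no DLTs, if the data are completely or quasi-completely separated (checked directly, not by the convergence flag), or if the estimated slope is not positive, the frequentist MTD is reported as not calculable. If the estimated 30% dose exceeds the highest tested dose, the result is reported as MTD not reached within the tested doses. In either case no MTD is named, and the observed DLT rate at the highest tested dose is given with an exact 95% confidence interval.

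In the 768 mg example the output would be not reached, with 0/6 at 60 mg and an upper exact limit of 1 − 0.025^(1/6) = 46%. That shows plainly how little is known at that dose.

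The cost is these sentences and a small change to the TLF-shell code. The downside is that the approach will name an MTD less often: in 2% (flat 5% curve) to 51% of simulated trials on the full grid. The unpenalised model can stay.
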